9.2 Exclusion Criteria

Subjects are excluded from the study if any of the following criteria apply:

 BD	Document Type: Global Clinical	Page No: 14 of 59
	Title: Clinical Investigation Plan Study ID: UCC-23AC023	Version No: 1.0

Template GFM-10095B

1. Has urinary retention
2. Incontinent to feces
3. Has any irritation, wound, open lesion at the device application site
4. For females: currently menstruating without use of an internal device, e.g. tampon or menstrual cup, during the execution of the study
5. For females: currently pregnant at time of consenting (self-reported)
6. Currently enrolled in or has previously been enrolled in or has completed nursing or other clinical training and courses
7. Has ever been employed as a home health aide or homecare provider
8. Any other condition that, in the opinion of the investigator, would preclude them from participating in the study.

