10.1 Screening and Enrollment Procedures

All participants will be screened against the inclusion and exclusion criteria (see section 9.1 & 9.2). Participants who fail to meet eligibility criteria must not have a study device placed.

The Investigator or their designee will explain the study to the participant, answer all of the participant's questions, and obtain written informed consent (and assent, as applicable) before the collection of any study data or performance of any study procedures.

 BD	Document Type: Global Clinical	Page No: 16 of 59
	Title: Clinical Investigation Plan Study ID: UCC-23AC023	Version No: 1.0

Template GFM-10095B

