1.7	
The HCP will perform a skin integrity check and note any existing signs or symptoms of irritation in the perineal area. If the participant's skin is compromised, the HCP will consult the site staff before proceeding with placement of study device and/or withdraw the participant.
 
HCP will confirm if no signs or symptoms of irritation in the perineal area was noted.

Steps	Activity 2 (Placement of device)
2.1	The participant will be given either the PureWick™ Male External Catheter (male participants only) or PureWick™ Flex Female External Catheter (female participants only).
2.2	For female participants only: The participant (or guardian/parent) or HCP will curve the PW Flex to fit the participant's anatomy per the IFU.
2.3	
The PW MEC or PW Flex will be connected to the canister via collector tubing per the IFU. Tubing connection to be done by the participant (or guardian/parent) for the self-placed void and by the HCP for the HCP-placed void. The HCP will confirm and record if the tubing connection was made correctly for the self-placed void. If the connection was not done correctly, the HCP will capture the reason:
 
 1. The participant did not understand how to make the connection 2. The participant connected the device to the wrong tubing port 3. The participant was not physically able to make the connection with sufficient force 4. Other, specify 
The HCP will adjust tubing connection prior to void if it was not done correctly.

2.4	Based off the randomization of placement sequence, the participant will self-place (or guardian/parent) the device or the HCP will place the device.
2.5	
If device was self-placed (or guardian/parent), the HCP will confirm the placement of the PureWick™ Male External Catheter (male participants only) or PureWick™ Flex Female External Catheter (female participants only). If the device is not placed correctly, the HCP will ask the participant to reposition/adjust the device. The HCP will record if any adjustments were made.
 
Even when placed correctly, participants may adjust the device as needed for comfort. The HCP will record if any adjustments were made.

Steps	Activity 3 (Void #1)
3.1	The HCP will confirm that the absorbent bed pad is appropriately positioned under the participant.
3.2	The participant will be asked to void in the supine position. The participant will be instructed not to strain or attempt to regulate their urine flow.

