Steps	Activity 4 (Removing the device)
4.1	
After the completion of the void the participant (or guardian/parent) or HCP (based off placement sequence) will carefully remove the device per the instructions for use.
 
 • For female participants, HCP will record if the device has dislodged after the void prior to device removal
4.2	The HCP will record whether they observed any urine leak from the device upon removal.

	Document Type: Global Clinical Title: Clinical Investigation Plan Study ID: UCC-23AC023	Page No: 18 of 59
		Version No: 1.0

Template GFM-10095B

4.3	The HCP will lift the catheter and tubing to make sure all the liquid flows into the canister.
4.4	The HCP will perform a skin integrity check and note any signs of irritation in the perineal area or adverse reactions. HCP will confirm if no signs or symptoms of irritation in the perineal area were noted.
4.5	The HCP will turn the PUCS suction OFF by flipping the black switch on the PUCS.
4.6	The used absorbent pad will be weighed by the HCP, and the value documented on the appropriate CRF. The canister (with lid) with urine will be weighed by the HCP and documented. The used catheter will be disconnected from the tubing and discarded.
4.7	The participant will be asked to complete all applicable questionnaires.
Steps	Activity 5 (Void #2)
5.1	After completion of void 1, the participant will be instructed to drink fluids in preparation for void 2.
5.2	Approximately 30 minutes after void 1 or when the participant feels the need to void again, the participant will proceed with void 2 (the participant will not use the same wetted device but a new clean device). Steps in Activities 1-4 will be repeated for the 2 nd void based off the placement sequence.
Steps	Activity 6 (After Completion of Both Voids)
6.1	Once the participant has completed both voids, the participant will be asked to complete the remaining required questionnaire.
6.2	Each HCP will complete the ease-of-use questionnaire after completing all study activities.

Questionnaires to be completed

Person to complete questionnaire	Questionnaire to complete	When to complete
Participant	Perception of wetness	After each void
Participant	Ease of use	After self-placement void
Participant	Comfort	After completion of all voids
Participant	IFU Evaluation	After self-placement void
HCP	Ease of use	After completion of all participants. Each HCP completes this questionnaire once per device.

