26.0 APPENDICES

26.1 Appendix 1 - PureWick™ Male External Catheter

en

Instructions for Use

Items needed for application (not included):

Trimmers or Clippers
 Soap and water wipes
 Drying towel

START HERE: Wash your hands before and after this procedure. If placing or removing this product on another person, wear gloves. Please read instructions, warnings, precautions, and recommendations entirely before placing the device.

Indications for use:

The device is intended for non-invasive urine output management, such as urinary incontinence, in users with male anatomy.

Contraindications:

- Users with urinary retention.

Warnings:

[figure not shown]
- Do not use on irritated skin. Examples include, but are not limited to, rashes, skin tears, or blisters.
- Do not cover fresh surgical wounds with the device.
- Do not use the device with any material or in any position that blocks the vents on the front of the device or does not allow for airflow through the device. Examples include, but are not limited to, tight clothing or briefs.
- To avoid potential skin injury, never pull the device directly away from the user. Always peel in the direction from head to foot.
- Stop use if an allergic reaction occurs.
- After use, this product may be a potential biohazard. Dispose of in accordance with applicable local, state, and federal laws and regulations.

Precautions:

- Not recommended for users who:
 - Are agitated, combative, or uncooperative and might remove the device.
 - Have frequent episodes of bowel incontinence without a fecal management system in place.
 - Have skin irritation or breakdown at the site.
- Do not use barrier creams, lotions, or ointments on the penis or pubic skin around the base of the penis when using the device. These may impede suction or weaken adhesive.
- Proceed with caution in users who have had recent surgery of the external male anatomy.
- Always check skin for irritation or breakdown and clean and dry the skin prior to placement of a new device.

Recommendations:

- Wash hands thoroughly before device placement.
- Ensure the device remains connected after turning the user, monitoring for pulling and tension on the device.
- Remove the device prior to walking.
- Check device placement and user's skin at least every 2 hours.
- Refer to the PureWick™ Urine Collection System IFU for instructions on suction tubing replacement.

[figure not shown]

SYMBOL	SYMBOL TITLE (STANDARD REFERENCE)	EXPLANATORY TEXT

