3. Trim or clip the pubic hair to ensure the product securely adheres to the skin. Check the skin and do not use if there is irritation or breakdown. Clean the penis and the skin around the base of the penis with soap and water or soap and water wipes. Dry skin prior to positioning the device.
NOTE: Moisture or soap residue on skin will weaken the adhesive.
4. Position the device, aligning drainage fitting towards the feet of the user. Slide the opening of the device over the penis until close to, but not touching, the skin around the base of the penis. Center penis within the opening. Do not place scrotum inside the device. Remove the bottom adhesive peel-off and press the device against the skin below the base of the penis. Remove the top adhesive peel-off and press the device against the skin above the base of the penis. Ensure device has fully adhered around the base of the penis by pressing down on the adhesive.

Removal of PureWick™ Male External Catheter

5. Gently lift the top edge of the adhesive base off the skin. In a slow, downward peeling motion, remove the device. If necessary, use a warm, wet cloth or pad to help loosen adhesive.
Warning: To avoid potential skin injury, never pull the device directly away from the user. Always peel in the direction from head to foot.
- After use, this product may be a potential biohazard. Dispose of in accordance with applicable local, state, and federal laws and regulations.

When to Replace PureWick™ Male External Catheter

6. Replace the device at least every 24 hours or if soiled with feces, blood, or semen.

Wall Suction

This product is compatible with wall suction in hospital-like settings. If using this set-up, connect the canister to wall suction and set to a minimum of 40 mmHg continuous suction. Always use the minimum amount of suction necessary.

BD, the BD Logo and PureWick are trademarks of Becton, Dickinson and Company, or its affiliate.
 © 2023 BD and its subsidiaries. All rights reserved.

 Manufacturer:
 C. R. Bard, Inc.
 [name]
 [name]
 [name]
 bd.com

	Document Type: Global Clinical	Page No: 35 of 59
	Title: Clinical Investigation Plan Study ID: UCC-23AC023	Version No: 1.0

Template GFM-10095B

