Users with urinary retention.

Warnings

- The PureWick™ Flex Female External Catheter is designed for single-use only. Trying to wash, sanitize or reuse it may lead to risk of infection or illness. This may damage the product and materials. The product may not work and cause injury or illness.
- To avoid potential skin injury, never push or rub the product against the skin during placement or removal.
- Do not block airflow to the product (e.g., blocking the vent hole, bedpan, barrier creams)
- Do not insert the product into vagina, anus, or other body orifice.
- Stop use if an allergic reaction occurs.
- After use, this product may be a potential biohazard. Dispose of in accordance with applicable local, state, and federal laws and regulations.
- Do not use on users with frequent episodes of stool incontinence without a fecal management system in place.
- Do not use on users with skin irritation or breakdown at the site.
- Use with caution on users who had recent surgery of the external female anatomy.
- Do not use on users with moderate/heavy menstruation who cannot use a tampon.

MRI Warnings

- Always disconnect the PureWick™ Flex Female External Catheter from wall suction or the PureWick™ Urine Collection System prior to an MRI procedure.
- It is important to closely follow these specific conditions that have been determined to permit the examination to be conducted safely. Any deviation may result in injury to the user.
- Non-clinical testing demonstrated that the PureWick™ Flex Female External Catheter is MR Conditional. A user with one of these PureWick™ Flex Female External Catheters can be scanned safely under the following conditions:

	Document Type: Global Clinical Title: Clinical Investigation Plan Study ID: UCC-23AC023	Page No: 36 of 59 Version No: 1.0
---	--	--

Template GFM-10095B

- Static magnetic field of 1.5-Tesla or 3-Tesla only
- Maximum spatial gradient magnetic field of 40-71m (4000-Gauss/cm)
- Maximum MR system reported whole body averaged specific absorption rate (SAR) of 2-W/kg for up to 60 minutes of continuous scanning in the Normal Operating Mode
- Under the scan conditions defined, the PureWick™ Flex Female External Catheter is expected to produce a maximum temperature rise of 1.5 degrees Celsius after 15-minutes of continuous scanning.
- There are no circularly polarized (quadrature-driven) RF coil restrictions.

Precautions

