Placement

- 4 Have the user lie on their back with knees bent and thighs apart (frog legged) or on their side before placing the product.

With their legs open, check the skin for irritation or breakdown, and clean the female anatomy.

NOTE: If skin irritation or breakdown is seen, do not use the product.

- 5 Spread the inner labia and keep them spread while placing the product.

With white wicking material side facing the user, place the bottom end of the product between the buttocks, but not as far back as to cover the anus.

Gently tuck white wicking material side between the inner labia, directly against the urethra (where the urine comes out).

NOTE: Make sure the urethra is at least one inch down from the top of the white wicking material.

- 6 Make sure the inner labia wrap around the product and are not tucked under it.

[figure not shown]
[figure not shown]
Once the product is in place, slowly close the legs and **make sure the vent hole is not covered**. See product diagram on page 1 for vent hole location.

NOTE: For users with **larger labia**, less of the product will be visible. For users with **smaller labia**, more of the product will be visible.

Removal

- 7 Open the legs and gently spread the labia. Gently pull the product away from the body. Keep suction on while removing the product.

After use, this product may be a potential biohazard. Dispose of in accordance with applicable local, state, and federal laws and regulations.

[figure not shown]

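### Step 1.7 leaves placement on compromised skin open after consultation; the main gap is before void 2, where both catheter IFUs forbid use but the eligibility rules do not clearly apply

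*Protocol*

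**What the plan says.** Step 1.7 of Protocol 10.4 comes after clipping of pubic hair in males (step 1.1) and cleaning (step 1.6), and just before placement. The HCP inspects the perineal area, and then: "If the participant's skin is compromised, the HCP will consult the site staff before proceeding with placement of study device and/or withdraw the participant". The protocol does not define *compromised* and gives no rule for what the consultation should decide. Step 5.2 carries the check over to the second void: "Steps in Activities 1-4 will be repeated for the 2" (the sentence continues with the second void).

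Four other places bear on the same situation:

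- Exclusion 3 (Protocol 9.2): "Has any irritation, wound, open lesion at the device application site".
- Protocol 10.1: "Participants who fail to meet eligibility criteria must not have a study device placed".
- Male catheter IFU (Appendix 1): "Do not use on irritated skin" among the warnings, and "Check the skin and do not use if there is irritation or breakdown" in placement step 3.
- Flex female catheter IFU (Appendix 2): "Do not use on users with skin irritation or breakdown at the site" among the warnings, and "If skin irritation or breakdown is seen, do not use the product" in the placement instructions.

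The collection-system IFU (Appendix 3) is softer: it advises against use when skin in the contact areas is irritated or broken down. Protocol 5.2 commits the study to following that IFU.

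There are two further skin checks. The schedule in Protocol 3.0 has the HCP look at the application area at baseline. Step 4.4 has the HCP inspect the perineal skin after each removal.

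**The concern.** The step that governs the moment before placement offers an outcome that other parts of the protocol rule out. An HCP who consults a colleague and then places the device on irritated skin has followed step 1.7 as written and has no reason to see a deviation.

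What is at stake is safety. A participant, possibly a minor, could have a device placed on irritated or broken skin against the labelling reproduced in the protocol's own appendices. Section 8.2.1 relies on those safeguards: for the female device it lists the IFU and the exclusion criteria as mitigations for skin injury, and for the male device it lists checking skin integrity before application. Section 9.3 requires the IRB to find no more than minimal risk to children. Listing 7 of the SAP would show such a placement afterwards but would not prevent it.

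**Working it through.** The plan states no figure on this point, so the check is a comparison of texts, followed by a count of how often the step applies.

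**Before void 2**

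1. One device has been placed and removed; the male device is adhesive (8.2.1). Void 2 follows about 30 minutes after void 1, or when the participant next needs to void (step 5.2).
2. Step 4.4 records irritation after removal but attaches no consequence to it.
3. Exclusion 3 and section 10.1 are entry rules. The participant was eligible when enrolled, and neither text clearly covers irritation that arises after the first void.
4. Step 1.7, repeated through step 5.2, is therefore the operative instruction, and it leaves placement open.
5. Both catheter IFUs say not to use the device in that state. The conflict is direct and nothing else in the protocol settles it: withdrawal for safety under 9.7.1.1 is discretionary.

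**Before void 1**

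1. A finding at the application site meets exclusion 3, and 10.1 then forbids placement without exception. Step 1.7 still leaves it open, so the conflict exists here too, and the catheter IFUs conflict in the same way.
2. The exposure is narrower. The baseline assessment looks at the application area, and step 1.1 starts only once baseline data are complete. What remains is mainly a finding that is new, for example after clipping, or one missed at baseline.

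**Area inspected.** Step 1.7 refers to the perineal area, whereas exclusion 3 refers to the application site. For the male device the site is pelvic skin around the base of the penis (8.2.1). Consultation has a sensible role for perineal findings away from the site, but the step does not limit it to those.

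**Number of occasions**

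- Planned checks: (20 male + 20 female) × 2 voids = 80, of which 40 are before void 1 and 40 before void 2.
- Checks in participants aged 12 to 17, if the 50% target in 9.0 is met: 0.5 × 40 × 2 = 40, of which 20 are before void 2.

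These count opportunities for the conflict. They are not expected events.

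**The case against.** The strongest reply is that the protocol, read as a whole, already gives the right answer before void 1. Section 10.1 is absolute, 10.4 admits only participants who meet no exclusion criterion, section 15.0 bars deviations, and an HCP has already looked at the application area at baseline. On this reading step 1.7 is a pause in which staff decide whether a perineal finding matters, and consultation is how 10.1 is applied. Most of that stands for void 1. It is why a reader should not infer that the protocol sets out to treat ineligible participants, or that step 1.7 is the only skin check.

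It does not dispose of void 2. Step 4.4 provides an inspection but no rule, the PI's power to withdraw is optional, and the baseline check cannot see what the first device caused.

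Two other points against are fair. The collection-system IFU only advises against use, so the firm prohibition rests on the two catheter IFUs. The count of 80 is the sample size times two and says nothing about how often skin will be affected. It can also be said that the sponsor classes the study as non-significant risk and that each device is worn for a single void. That limits the likely harm but does not reconcile the texts.

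**Conclusion.** Step 1.7 is wrong as written: it permits a placement that both catheter IFUs prohibit. The main gap is the 40 planned checks before void 2, where no other protocol rule clearly forbids placement. At the 40 checks before void 1 the wording also contradicts exclusion 3 and 10.1, but those rules and the baseline assessment limit the practical exposure to new or missed findings.

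This should be fixed as a safety inconsistency. Two stronger conclusions might be inferred and are not supported. The documents give no rate of irritation or breakdown, so no number of affected participants can be stated. Nor do they show any effect on the capture-rate summary. The conclusion rests on taking *and/or* at its plain meaning, so that withdrawal is one option among others, and on reading the eligibility criteria as conditions at entry.

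**What to change.** Reword step 1.7 along these lines:

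- If irritation, a wound, an open lesion or skin breakdown is seen at the device application site, the device is not placed.
- If this is found before the first placement, the participant is withdrawn. If it is found before void 2, the second void is omitted.
- Consultation with site staff is kept only for perineal findings outside the application site, and placement may then follow only where the device IFU permits use.

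Leave the step where it is, after clipping and cleaning and immediately before placement.

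The change is to the wording of one step, with no new procedure. Tables 5 to 7 of the SAP already have rows for skin signs before placement and for whether the device was placed.

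The cost is lost data. An unknown number of participants could lose one or both voids; transient redness after removal of the adhesive male device might be one cause, and its frequency is not given. Lost participants are not replaced (9.5.1), while 11.1 sets a minimum of 20 per sex: with exactly 20 enrolled, one withdrawal before placement leaves 20 − 1 = 19 treated. Such a participant is also outside ITT (11.2). A participant whose second void is omitted stays in ITT but contributes to only one placement group in SAP Tables 9a, 9b and 11. If the omitted void was the self-placed one, the participant ease-of-use and IFU questionnaires are lost as well. The amended text should say whether the comfort questionnaire, due after all voids, is still completed after a single void. The catheter IFUs already rule out the voids given up for irritation or breakdown at the site.

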10.5 Safety Assessments

All AEs will be captured and summarized.

10.6 Follow-up Procedures

After all study assessments and procedures are complete, the participant will be discharged from the study. The participant will be asked to report any discomfort or voiding issues occurring within the first 24 hours after discharge from the study to the PI.

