3.0 STUDY SCHEDULE

Visit	Study Activity	Activity
Visit 1	Obtain Consent	Obtain consent for study participants. For minor participants, consent will be obtained from the participant's parent or guardian and assent provided by the minor participant.
	Screening & Randomization	Screen potential participants against the inclusion and exclusion criteria. Randomly assign participants to placement sequence
	Baseline	Collect participant demographic data including height and weight. HCP completes a visual assessment of the skin in the device application area.
	Device use and urine measurement collection	After enrollment and randomization, train the participant to the device IFU. Prior to device placement, HCP assembles and sets up the PUCS. The study device will then be placed by the HCP, participant (or guardian/parent) per the assigned placement sequence. Placement will be confirmed by the HCP and then participant will void. Post-void, the device will be removed by the HCP, participant (or guardian/parent) and bed pad and canister weights will be captured. Above steps will be repeated for void 2.
	Questionnaires	Participants complete the questionnaires below. 
 • Perception of wetness • Ease of use • Comfort • IFU Evaluation After completion of all participants, each HCP completes this questionnaire once per device.
	Participant Completion	Participants will be discharged from the study after completing all study activities.
	Study Completion	End of study is when the last study participant is discharged.

	Document Type: Global Clinical	Page No: 5 of 59
	Title: Clinical Investigation Plan Study ID: UCC-23AC023	Version No: 1.0

Template GFM-10095B

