8.2.1 Anticipated Adverse Device Effects

Potential Risk of Clinical Significance	Summary of Data/Rationale for Risk	Mitigation Strategy
PureWick™ Flex Female External Catheter		

 Skin Injury Skin Irritation Allergic reaction Inflammation Infection Discomfort 	The PureWick™ Flex is a flexible, contoured external catheter (a "Wick" that is positioned between the separated gluteus and labia, against the urethra.	
 To avoid potential skin injury, never push or rub the product against the skin during placement or removal. Assess local area before application/after device removal and periodically throughout use. Participants are allowed to discontinue use if they feel any pain or discomfort. IFU (warning, contraindications, instructions) Study Exclusion criteria

 Tissue injury or possible minor bleeding 	The device sites against the skin, sticking and possible minor bleeding is a potential risk.	
 Top layer of wicking material has been selected to minimize the possibility of sticking to skin.

 Exposure to Biohazard or bloodborne pathogens 	Device is intended to capture urine, may lead to transmission of bloodborne pathogens.	
 HCP will wear gloves when handling devices and will dispose of used devices per the IFU

 Injuries 	Device is labeled MRI conditional. Potential interference with other medical devices or treatments under specific operating conditions.	
 IFU (warnings) No MRI included in the study procedures.
PureWick™ Male External Catheter		

 Skin injury Skin Irritation Allergic reaction Infection Discomfort 	
 PureWick™ MEC is an external device placed around the base of the penis and adhered to the pelvic skin. 	
 To avoid potential skin injury, never pull the device directly away from the patient. Always peel in the direction from head to foot. Perform perineal care using the included wipes and assess skin integrity before device application. Assess the device placement and patient's skin at least every 2 hours.

 BD	Document Type: Global Clinical	Page No: 12 of 59
	Title: Clinical Investigation Plan Study ID: UCC-23AC023	Version No: 1.0

Template GFM-10095B

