9.6 Study / Participation Duration

- 9.6.1 It is expected to take approximately 2-3 weeks to complete subject enrollment. The total duration of the study is expected to be 2-3 weeks (last subject, last visit).
- 9.6.2 The duration of study participation for an individual subject is expected to be approximately 2-3 hours (enrollment through last study assessment).

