9.7.2 Lost to Follow-Up

The study only has one visit with two voids. There are no follow-up visits.

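### The 24-hour post-discharge safety request omits most of the effects the protocol anticipates, and the study is declared ended before that window closes

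*Protocol*

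**What the plan says.** **After discharge.** Protocol section 10.6 says that the participant, once discharged, will be "asked to report any discomfort or voiding issues occurring within the first 24 hours after discharge from the study to the PI". Section 9.7.2 confirms that nothing further is scheduled: "The study only has one visit with two voids. There are no follow-up visits". Neither document describes a call, message, diary or return check.

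**Anticipated effects.** For the female device, the first entry in section 8.2.1 starts with skin injury and continues "Skin Irritation Allergic reaction Inflammation Infection Discomfort". The male device has the same list without inflammation. A further entry for the female device covers tissue injury or minor bleeding.

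**On-site checks.** Section 10.4, step 4.4, reads: "The HCP will perform a skin integrity check and note any signs of irritation in the perineal area or adverse reactions". Step 1.7 is a skin check before placement. Step 5.2 repeats Activities 1 to 4 for the second void, so both checks are done twice.

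**Adverse event capture.** Section 10.5 commits to capturing and summarizing every adverse event but states no collection window. SAP section 2.3 plans a listing only.

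**End of participation and of study.** Section 3.0 says "Participants will be discharged from the study after completing all study activities" and "End of study is when the last study participant is discharged". Section 7.5 treats a participant as complete once all the procedures in Section 10.0 are done, and dates the end of study to the last participant's last visit. Section 9.6 puts individual participation at "approximately 2-3 hours (enrollment through last study assessment").

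**The concern.** Section 7.2 says that the study will evaluate device safety as well as performance in adolescents and that the evidence will support a wider indication. A listing with few or no adverse events will therefore be used as evidence. What it can show depends on what participants were asked, for how long, and whether silence means that nothing happened.

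The request is narrower than the protocol's own list of anticipated effects, and it relies on the participant to come forward. A participant who notices redness or a rash that does not hurt has been given no reason to report it. The 24-hour window also runs past the point at which section 3.0 declares the study over, so the text leaves unclear whether a next-day report belongs to the study's safety data.

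**Working it through.** The plan gives no figure to reproduce here: no event rate, onset time or adverse event window. The check sets the provisions side by side.

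**1. What is asked against what is anticipated**

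| Effect in section 8.2.1 (main entry per device) | Device | Named in the 10.6 request? |
|---|---|---|
| Discomfort | both | yes |
| Skin injury | both | no; covered only if felt as discomfort |
| Skin irritation | both | no; covered only if felt as discomfort |
| Allergic reaction | both | no; covered only if felt as discomfort |
| Infection | both | no; covered only if it causes discomfort or affects voiding |
| Inflammation | female | no; covered only if felt as discomfort |

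One of six effects for the female device and one of five for the male device is named. The others come within the request only when they cause discomfort or a voiding problem.

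**2. When the skin is examined**

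- Before the first placement: step 1.7.
- After the first removal: step 4.4.
- Before the second placement: step 1.7, repeated under step 5.2. The second void follows about 30 minutes after the first, or when the participant needs to void, so this check is also a later look at skin exposed to the first device.
- After the second removal: step 4.4, repeated under step 5.2.
- From then on: none described.

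The SAP tabulates the findings before placement and after removal (Tables 5 to 7), so the on-site part is well covered. The gap begins after the second removal.

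**3. When the study ends against when the window closes**

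Take the last participant and set discharge at hour 0.

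- End of study under section 3.0: hour 0.
- Close of the 10.6 window: hour 24.
- Difference: 24 − 0 = 24 hours in which reports are requested after the stated end of study.

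Section 7.5 does not settle this. Section 10.0 contains 10.6, so participant completion can be read as including the 24-hour request. Yet 7.5 dates the end of study to the last visit, and there is only one visit. On that reading the study would end before its last participant had completed it.

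**4. Who is asked, and what the listing would show**

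Section 9.0 targets half of the 40 participants in the 12–17 age range: 0.5 × 40 = 20. The 10.6 request is addressed to the participant and gives the parent or guardian no part. SAP Listing 17 shows start and end dates but no indicator relative to discharge. An event dated on the visit day could therefore have begun before or after the participant left.

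**The case against.** The strongest case against is that this is a small gap in wording. Much of that case stands.

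- **Late reports are not barred.** Section 19.1.1 defines an adverse event as any untoward medical occurrence, section 10.5 promises to capture all of them, and section 19.3.1 sets the investigator's reporting duty with no cut-off at discharge. A reader might infer that a next-day rash could not be recorded because the participant is closed. The documents do not say so: 10.6 limits what is prompted, not what the site must record.
- **Observation is not confined to the minutes around removal.** That reading overlooks the repeat of step 1.7 before the second placement.
- **Discharge is named as the end of study only in section 3.0.** Sections 7.5 and 9.6 refer to the last visit and the last assessment.
- **No size can be given.** A reader might want to state the share of post-use time without active ascertainment, or how a missed event would change a reported rate. The first needs the time on site after final removal, which is not given; the 2–3 hours run from enrollment. The second assumes an event rate, and the SAP plans no rate table for adverse events.
- **Delayed onset is not documented.** Section 8.2.1 lists effects without onset times. That some will appear after discharge is a possibility, not a finding.
- **Proportionality.** The devices are Class I exempt and marketed, the study is classed as non-significant risk, exposure is one void per placed device, and section 6.1 includes no safety endpoint. The consent form is not among the documents reviewed and may say more about what to report.

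These points limit how serious the issue is. They do not explain why the request omits effects that the protocol itself lists, and they do not reconcile section 3.0 with 10.6.

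**Conclusion.** The point holds as a mismatch between provisions, worth correcting because correction costs so little. The post-discharge request in 10.6 is narrower than the effects anticipated in 8.2.1 and the commitment in 10.5. After the second removal no later check or site contact is described, so a visible but painless effect appearing after discharge is not prompted for, and silence cannot be distinguished from absence of an event. Sections 3.0, 7.5, 10.5 and 10.6 must be reconciled on when adverse event collection, participation and the study end.

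The number of events that might be missed cannot be quantified from the documents. The documents do not support saying that late events would be excluded, that effects are known to be delayed, or that safety was observed only around removal. The conclusion assumes that no other document seen by participants, such as the consent form, already widens the request.

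**What to change.** 1. **Section 10.6:** widen the request to match 8.2.1: any skin change, allergic reaction or sign of infection, as well as discomfort or voiding issues. For minors, direct it also to the parent or guardian. Align the consent form if it lists what to report.
2. **Sections 3.0, 7.5 and 10.5:** state that adverse event collection runs from consent to the close of the existing 24-hour window, and date participant completion and end of study there. Bring the participation time in 9.6 into line.
3. **Preferably:** close the window with one brief phone or text contact by existing site staff, and report how many participants were reached.
4. **SAP Listing 17:** add a flag for onset before or after discharge.

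The cost is protocol wording, one listing column, about 40 short contacts if item 3 is adopted (20 + 20 participants), and an end of study one day later. No visit or procedure is added. Anything that first appears after 24 hours would still not be asked about. Whether 24 hours is long enough is a clinical decision, and no change to it is proposed here.
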